# 1.0 SCHEMA

Total Number of Patients: 15

Olaparib is taken 300 mg BID orally

Ascorbate is given 1 g/kg, 2 times per week intravenously (first three doses [over 1.5 weeks]: titrate 0.25 g/kg, 0.5 g/kg, and 0.75 g/kg. Starting with cycle 1 week 2, the dose of Ascorbate will be 1 g/kg as long as this dose is tolerated)

# 2.0 OBJECTIVES

# 2.1 Primary Objective

To estimate the proportion of patients with metastatic castration resistant prostate cancer (mCRPC) having a 50% reduction in PSA from baseline (PSA50 response).

# 2.2 Secondary Objectives

- 1) To evaluate the safety and tolerability of olaparib in combination with IV ascorbic acid in patients with mCRPC.
- 2) To estimate the median time to PSA doubling from baseline of patients with mCRPC receiving olaparib in combination with IV ascorbic acid.
- 3) To estimate the median radiographic progression free survival (rPFS) of patients with mCRPC receiving olaparib in combination with IV ascorbic acid.
- 4) To estimate the median PSA progression free survival (PSA PFS) of patients with mCRPC receiving olaparib in combination with IV ascorbic acid.
- 5) To assess overall survival (OS) in patients with castration resistant prostate cancer.

# 2.3 Exploratory Objectives

Examine correlates that may be predictive of PSA50 response and rPFS.

- 1) To quantify ctDNA and perform mutational analysis in the peripheral blood and compare it to any baseline germline or somatic mutations (document prestudy on case report form).
- 2) To quantify circulating tumor cells (CTCs) in the peripheral blood at baseline, 4 weeks, 12 weeks, and upon progression and assess γH2AX foci in CTCs.
- 3) Optional yH2AX foci FFPE biopsy tissues.
- 4) To measure F2-isoprostanes in the urine as a pharmacodynamic measure of oxidant injury at baseline, 4 weeks, 12 weeks, and upon progression.
- 5) To measure 8-oxo-2'-deoxyguanosine as a measure of oxidative stress in the urine at baseline, 4 weeks, 12 weeks, and upon progression.

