- Vital signs will be collected prior to infusion. Vital signs include temperature, blood pressure, respiration rate, and heart rate. Height is collected prestudy only. There is a -3 day window of day 1 of each cycle that the vital signs can be collected within.
- 6 Clinical Hematology: CBC with differential ANC, ALC, AEC, and platelet count; Serum Chemistry: sodium, potassium, chloride, bicarbonate, glucose, BUN, creatinine, ALT, AST, alkaline phosphatase, total bilirubin, total protein, albumin, calcium.
- Safety labs and PSA may be collected within a window of up to 3 days prior to scheduled visit/dosing. As of Cycle 2 and further cycles: at Day 1 visit, hematology and chemistry should be collected per hold parameters; at Days 8, 15, and 22 visits, only chemistry will be collected per hold parameters (hematology does not need to be drawn on Days 8, 15, and 22 unless clinically indicated). After C1D1, PSA is collected at CnD1 only (i.e., not weekly).
- 8 Urine creatinine will be collected at C1D1, C2D1 (4 weeks), C4D1 (12 weeks), and at EOT.
- G6PD testing: Red blood cell hemolysis may occur in people found to be deficient in the G6PD enzyme.
- Up to 50mL of whole blood will be collected for ctDNA analysis at each time point. Blood samples should be drawn at screening (or pre-dose C1D1), C2D1 post infusion (4 weeks), C4D1 (12 weeks) post infusion, and at EOT. Bloods do not need to be collected at C1D1 if they were collected within 7 days prior to the visit. γ H2AX will also be assessed at C1D1, C1D8, C2D1, C4D1 and progression.
- Urine samples of up to 15mL will be collected to assess F2-isoprostanes and 8-oxo-2'-deoxyguanosine at screening (or pre-dose C1D1), C2D1 (4 weeks), C4D1 (12 weeks), and at EOT. Urine samples do not need to be collected at C1D1 if they were collected within 5 days prior.
- 12 Research samples will be collected at the discretion of the PI based on availability of supplies and safety of patient and staff. An optional biopsy at baseline and at C4D1 (+/- 2 weeks) will be performed to look for γH2AX in tissue.
- CT scan (chest/abdomen/pelvis or MRI if patient has contrast allergy) and bone scan to be assessed at baseline and every 12 weeks (+/- 1 week), and at EOT (if clinically indicated by PI/Sub-I).

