- In order to minimize the need for research-only in-person visits, telemedicine visits may be substituted for in-person clinical trial visits or portions of clinical trial visits where determined to be appropriate and where determined by the investigator not to increase the participants risks. Prior to initiating telemedicine for study visits, the study team will explain to the participant what a telemedicine visit entails and confirm that the study participant is in agreement and able to proceed with this method. Telemedicine acknowledgement will be obtained in accordance with the Guidance for Use of Telemedicine in Research. In the event telemedicine is not deemed feasible, the study visit will proceed as an in-person visit. Telemedicine visits will be conducted using HIPAA compliant methods approved by the Health System and within licensing restrictions.
- There is a -7 day window to draw C1D1 labs.
- The EOT visit must occur within 28 days of the last dose of ascorbic acid or olaparib, whichever is later.

- Subjects who discontinued study treatment without documented disease progression should continue to be monitored for disease status by radiologic imaging. Disease monitoring should continue to be assessed every two months (+/- 2 weeks) until: 1) start of a new antineoplastic therapy (information of the new cancer therapy will be collected), 2) disease progression, 3) death, 4) withdrawal of consent, or 5) study closure, whichever occurs first. Survival status and subsequent therapies will be collected during long term follow-up (LTFU) every 6 months (+/- 4 weeks) from the date of last treatment, by phone or chart review, for 3 years or until study closure. Gather date of death, date of radiographic and/or PSA progression, start and stop dates for subsequent therapies.
-  INR and PT/APTT will be performed at baseline and at subsequent timepoints if clinically indicated.

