#### 11.3 Urine Studies

Urine for measuring F2-Isoprostanes and 8-OHdG (markers of oxidative stress) will be collected at Screening, 4 weeks (C2D1), 12 weeks (C4D1), and at EOT - see study calendar for details. Baseline sample at screening should be collected before patient receives study drug. Complete instructions for the collection, processing, and shipment of samples will be provided in a separate lab manual.

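### The last correlative sample is set at progression in the objectives but at end of treatment in the calendar, so it can come from men who have not progressed and can be off drug

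*Combined protocol and SAP*

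**What the plan says.** The objectives tie the last correlative sample to progression. Section 2.3 plans "To quantify circulating tumor cells (CTCs) in the peripheral blood at baseline, 4 weeks, 12 weeks, and upon progression", with γH2AX foci to be assessed in those cells. It measures urinary F2-isoprostanes as a marker of "oxidant injury at baseline, 4 weeks, 12 weeks, and upon progression", and sets the same schedule for 8-oxo-2'-deoxyguanosine. Section 13.1 repeats these objectives, and Section 11.2.1 names a progression plasma sample for ctDNA.

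The operational text says EOT. Calendar footnote 10 in Section 7.1 states for blood: "Blood samples should be drawn at screening (or pre-dose C1D1), C2D1 post infusion (4 weeks), C4D1 (12 weeks) post infusion, and at EOT". The same footnote then says that γH2AX "will also be assessed at C1D1, C1D8, C2D1, C4D1 and progression". For urine, Section 11.3 states that samples "will be collected at Screening, 4 weeks (C2D1), 12 weeks (C4D1), and at EOT", in line with calendar footnote 11. Section 11.2 uses EOT for ctDNA, CTCs and γH2AX in CTCs, and Section 7.4.2 lists research blood and urine at the EOT visit.

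On timing, the calendar states: "The EOT visit must occur within 28 days of the last dose of ascorbic acid or olaparib, whichever is later".

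**The concern.** EOT and progression are different events. Section 7.4 lets treatment stop for unacceptable toxicity, intercurrent illness, withdrawn consent, noncompliance or investigator judgement, as well as for progression. A site that follows the calendar will draw the final research sample from any of these men and will have nothing to draw later if the disease then progresses.

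Two uses of the data are exposed. Section 11.2.1 hopes that ctDNA will reveal new mutations and mechanisms of resistance, which needs samples from men who have in fact progressed. The oxidative-damage and γH2AX markers are meant to show what the drugs do, and a sample taken after the drugs have stopped does not answer the same question as one taken on treatment. Section 13.6 gives the importance of the correlative data as one reason for having no futility monitoring, so it matters that those data can be interpreted.

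**Working it through.** The documents state no sample size, power or error rate for the correlative time points, so there is no figure to reproduce. The check is a comparison of the text.

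**Step 1. Last time point by section.**

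| Place | Samples | Last time point |
|---|---|---|
| 2.3, repeated in 13.1 | CTCs (with γH2AX), both urine markers | progression |
| 11.2.1 | ctDNA plasma | progression |
| 7.1, footnote 10 | blood | EOT |
| 7.1, footnote 10, closing sentence | γH2AX | progression |
| 7.1, footnote 11 | urine | EOT |
| 7.4.2 | research blood and urine | EOT |
| 11.2 | ctDNA, CTCs, γH2AX in CTCs | EOT |
| 11.3 | urine | EOT |

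The calendar grid has no progression visit. A site can meet both wordings only when EOT and progression happen to coincide.

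**Step 2. Who reaches EOT.** Section 7.4.2 triggers the visit by treatment discontinuation, and the reasons in Section 7.4 include several that are not progression. The EOT set can therefore contain men who have not progressed.

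**Step 3. The converse gap.** Under Section 7.5, men who stop without documented progression are followed by imaging every two months. The long-term follow-up column of the calendar shows no research blood or urine. If such a man progresses later, no progression sample is scheduled.

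**Step 4. Time off drug.** EOT falls 0 to 28 days after the last dose of whichever drug stopped later. Section 8.1 lets one drug continue while the other is withheld, so the gap from the earlier-stopped drug can be longer. The gap varies between men and may be near zero.

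**Step 5. Comparability with earlier samples.** Blood at C2D1 and C4D1 is specified as post infusion in footnote 10 and Section 11.2. The EOT blood draw has no such link to an infusion, so it is not like-for-like. Urine has no infusion timing at any visit, so for urine the difference is only on treatment versus possibly off treatment.

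**Step 6. Does the analysis separate these samples?** Section 13.9 describes patterns over time, paired pre/post comparisons and a search for predictors of response. It has no rule separating progression from other EOT samples, or on-drug from off-drug samples.

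**Step 7. Scale.** No rate of stopping without progression is given. What can be stated is the weight of one such sample if every man contributes a final draw: 1/12 = 8.3% of the set with 12 men, or 1/15 = 6.7% with 15. That is a weight per sample and not an estimate of how many there will be.

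**The case against.** The strongest reply is that this is loose terminology in descriptive work. Section 7.4.1 encourages treatment until radiographic progression or PSA doubling requires new therapy, so in many men EOT may fall close to progression. The reason for and date of removal go on the case report form (7.4), dose interruptions are recorded (8.2.2.3) and progression dates are collected in follow-up (7.5.1), so samples could be sorted afterwards. Detailed collection instructions are in a laboratory manual that is not part of these documents. Section 13.9 specifies no contrast between week 12 and progression.

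Much of this stands, and it keeps the point minor. It does not remove it: the sections still disagree, later progressors still have no scheduled sample, nothing tells the analyst to sort the samples, and the timing of a draw cannot be corrected once it is taken.

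Four stronger readings are tempting, and the documents do not support them.

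- A reader might take the 3 extra men in 15 (3/15 = 20%) as the share of EOT samples that are not at progression. Sections 3.0 and 13.5 give those places as an allowance for replacing early drop-outs. An early drop-out may give no EOT sample, and a man who stops later for toxicity need not be among the 3.
- A reader might put a figure on wash-out from an assumed marker half-life. The documents give no half-life for any of these markers.
- A reader might conclude that every final sample is off drug, or that wash-out will be reported as resistance. The 28 days is an upper limit, and no planned analysis draws that inference.
- A reader might extend the post-infusion mismatch to urine. Only blood carries that timing.

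**Conclusion.** The inconsistency is real and can be verified from the text alone. As written, the final correlative sample can come from men who have not progressed and can be off drug. The final blood sample is not comparable in timing with the C2D1 and C4D1 samples, and men who progress after stopping for another reason have no scheduled progression sample.

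The size cannot be stated, because it depends on how many men stop without progression and how fast each marker falls off drug, and the documents give neither. The conclusion needs no assumption about either quantity; it rests on the stopping criteria in Section 7.4 and the EOT window. The consequence is confined to the exploratory analyses. The primary endpoint, the decision rule for 12 men and the safety monitoring rule do not use these samples. This is a minor point, worth correcting while samples are still to be drawn.

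**What to change.** 1. Reconcile Sections 2.3, 7.1 (including both sentences of footnote 10), 11.2, 11.2.1, 11.3 and 13.1 to one defined final time point, and bring 7.4.2 into line. Take the final research blood and urine at the existing visit where progression is documented, when that is feasible without altering treatment timing, and otherwise at EOT. Say which visit counts when progression needs confirmation, since Section 7.4.1 requires a second PSA value at least 4 weeks apart and allows an unclear bone scan to be repeated in 6 weeks.
2. Record with each final sample the reason for EOT, the progression status at the draw, and the days since the last dose of olaparib and of ascorbic acid.
3. In Section 13.9, analyse as progression samples only those from men with documented progression, and report off-drug samples separately from the on-treatment pharmacodynamic comparisons.

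The cost is wording in these sections and a few data fields, most of which can be filled from what is already recorded. No treatment rule changes. The downside is slightly fewer samples in the progression comparison. Men who stop early and progress later would still lack a progression sample unless a draw were added in follow-up, and the report should say so.

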#### 3.0 STUDY DESIGN

This is a multi-center phase II study to evaluate the safety and clinical activity of the combination of olaparib and high-dose IV ascorbate, as second or later line of therapy, in castration resistant prostate cancer patients with no known DNA repair gene mutations (DDRm). In brief, the primary endpoint is  $PSA_{50}$  response, defined by a 50% reduction in PSA from baseline. The secondary endpoints are assessing the PSA doubling time, radiographic and PSA PFS, safety and tolerability as defined by the incidence of grade 3 to 5 toxicities, and measuring overall survival. For complete endpoint definitions, see **Sections 13.2-13.4**. The total accrual for this clinical trial will be 12 men with castration resistant prostate cancer (n=12).

Olaparib will be administered at 300 mg PO BID; ascorbate will be administered at 1 g/kg IV twice weekly at least 24 hours apart until objective disease progression or unacceptable toxicities or patient withdrawal for other reasons.

The study will consist of a screening period (within 28 days of the first dose), treatment period, and follow-up period. Dose reductions are allowed per **Section 8.2.** Enrollment will continue until 15 subjects (allows for 3 drop outs) have received at least one dose of study treatment.

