# 13.5 Sample Size/Accrual Rate

Accrual to this study is expected to be one patient per month. For this combination to be considered for further study a  $PSA_{50}$  response of 23% or more would be desirable. Our null hypothesis of 3% is based on the low  $PSA_{50}$  response rate, 3% (1 of 33), reported by Mateo et al. for this patient population. This single-stage design has a 95% chance ( $\alpha$  = 0.05) of rejecting the therapy if the true percentage of patients with some benefit from treatment is less than or equal to 3% and an 80% chance of concluding the therapy is beneficial if the true percentage is 23% or more. Twelve patients, will be assessed for 6 months and if 2 or more achieve a  $PSA_{50}$  response, the therapy will be considered for a larger study. Patients enrolled who never receive any study related therapy will be

replaced. Enrollment would be allowed to continue, up to a maximum of 15 patients, to replace those patients that drop-out early.

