# 13.6 Futility and Safety Monitoring Plan

Given the small number of patients and the importance of obtaining correlative data to consider during the final evaluation of the study results, there will be no futility monitoring for efficacy during this pilot study. The trial will however employ a standard safety monitoring plan for adverse events. In addition, if any patient is diagnosed with an adverse event of special interest: myelodysplastic syndrome, acute myeloid leukemia, new primary malignancy (other than MDS/AML) or pneumonitis during the trial, the trial will be paused for a safety review.

Toxicity will be monitored continuously for grade 3-4 adverse events that do not resolve to grade 2 following four-weeks drug discontinuation (per section 8.1). The stopping rule is based on the posterior probability that the combination of treatments is too toxic. If the rate of these toxicities convincingly exceeds 30%, the study PI will hold enrollment if the posterior probability of risk greater than 0.30 is 65% or higher. The prior for this toxicity monitoring rule is beta (2,6). This corresponds to assuming our prior guess for the toxicity rate is 25%, and there is 90% probability that this proportion is between 5% and 52%.

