## 13.7 Analysis of Primary Endpoint

The primary endpoint is based on  $PSA_{50}$  response. All patients who receive at least one dose of olaparib and IV ascorbic acid will be evaluable for the primary objective. If patients do not have adequate PSA data after the initiation of therapy due to stopping for toxicity or withdrawing consent, then they will be considered unevaluable. The  $PSA_{50}$  response will be calculated as a proportion with 90% confidence intervals.

**PSA**50 **response** will be defined as a decrease in the PSA to 50% less than the baseline PSA upon enrollment in the trial. Patients must receive at least one dose of olaparib and IV ascorbic acid to be considered evaluable. After the initial measurement showing a >50% decrease in PSA compared to baseline, a second measurement must confirm the decrease,

and the measurements must be at least 4 weeks apart.  $PSA_{50}$  response rate will be calculated as a proportion with 90% confidence intervals.

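### The 2-responder go rule is sized for 12 evaluable patients, but Section 3.0 enrols until 15 are dosed; with 13 to 15 analysed no rule is given, and a cut-off of 2 has alpha 0.056 to 0.073

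*Combined protocol and SAP*

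**What the plan says.** The numbers appear in four places.

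- Section 1.0 (Schema): "Total Number of Patients: 15".
- Section 3.0 (Study Design) gives two numbers. One sentence reads "The total accrual for this clinical trial will be 12 men with castration resistant prostate cancer (n=12"). A later one reads "Enrollment will continue until 15 subjects (allows for 3 drop outs) have received at least one dose of study treatment". The second does not depend on a drop-out having occurred; the bracket only explains why 15 was chosen.
- Section 13.5 (Sample Size/Accrual Rate) holds the only decision rule: "Twelve patients, will be assessed for 6 months and if 2 or more achieve a" PSA50 response, the combination is considered for a larger study. Patients who never receive any study therapy are replaced. It adds: "Enrollment would be allowed to continue, up to a maximum of 15 patients, to replace those patients that drop-out early". Dropping out early is not defined.
- Section 13.7 (Analysis of Primary Endpoint) defines who is analysed: "All patients who receive at least one dose of olaparib and IV ascorbic acid will be evaluable for the primary objective". The exception is a patient without adequate PSA data "due to stopping for toxicity or withdrawing consent, then they will be considered unevaluable". It sets no maximum of 12 and does not mention the go rule.

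For safety, Section 13.6 sets out a posterior-probability rule ("The prior for this toxicity monitoring rule is beta (2,6"), with a 65% threshold for a toxicity risk above 0.30). Table 9 lists its boundaries up to 12 patients only.

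**The concern.** The error rates in Section 13.5 belong to one pair of numbers: 12 patients and a cut-off of 2. If Section 3.0 is followed literally, 15 patients are dosed, and Section 13.7 then counts all of them except those it calls unevaluable. The number analysed is 12 only by chance.

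Section 13.5 read alone does not close the gap. A patient who leaves early because of progression, or who leaves with adequate PSA data, could be replaced as an early drop-out and still be evaluable under Section 13.7. More than 12 can therefore be analysed even under the narrower enrolment wording.

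Two things are at stake. First, the promised 95% chance of rejecting an inactive combination fails at every size from 13 to 15 if the cut-off stays at 2. Second, the team could decide after seeing the data whether the denominator is 12 or all evaluable patients. With a cut-off of 2, a single responder among patients 13 to 15 can change the decision.

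**Working it through.** **Inputs.** Null rate p0 = 0.03, target rate p1 = 0.23, n = 12 and cut-off 2 (Section 13.5); exact single-stage design (Section 13.1); up to 15 dosed (Sections 1.0 and 3.0).

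**Formula.** The probability of a go decision with n patients and response rate p is

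P(X ≥ 2) = 1 − (1−p)^n − n·p·(1−p)^(n−1).

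**The plan's own figure first (n = 12).**

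- Alpha: 1 − 0.97^12 − 12 × 0.03 × 0.97^11 = 1 − 0.6938 − 0.2575 = 0.0486.
- Power: 1 − 0.77^12 − 12 × 0.23 × 0.77^11 = 1 − 0.0434 − 0.1557 = 0.8009.

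The stated design reproduces. It is also the smallest n that meets alpha ≤ 0.05 and power ≥ 0.80.

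**Same cut-off, other sizes.**

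| Analysed n | Alpha at 3% | Power at 23% |
|---|---|---|
| 10 | 0.035 | 0.71 |
| 11 | 0.041 | 0.76 |
| 12 | 0.049 | 0.80 |
| 13 | 0.056 | 0.84 |
| 14 | 0.065 | 0.87 |
| 15 | 0.073 | 0.89 |

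Using 1/33 instead of the rounded 3%, alpha at 13, 14 and 15 is 0.057, 0.066 and 0.074.

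**Raising the cut-off afterwards does not help.** With 3 responders required, alpha is 0.006, 0.008 and 0.009 at n = 13, 14 and 15, but power is only 0.60, 0.66 and 0.71. No whole-number cut-off at these sizes meets both stated targets.

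**How likely is more than 12?** Suppose 15 are dosed and each is independently unevaluable with probability u. The value of u is an assumption; the plan's own allowance is 3/15 = 20%. The analysed n is then Binomial(15, 1−u), and alpha is averaged over it.

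| u | P(more than 12 analysed) | Averaged alpha |
|---|---|---|
| 5% | 96% | 0.067 |
| 10% | 82% | 0.061 |
| 20% | 40% | 0.049 |

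**Safety tables.** After s events in N patients the posterior is Beta(2+s, 6+N−s). Stopping when P(risk > 0.30) ≥ 0.65 reproduces every Table 9 boundary for N = 2 to 12. Continued to N = 13, 14 and 15, 5 events give 0.608, 0.551 and 0.494 (continue) and 6 events give 0.772, 0.723 and 0.671 (stop). The plan's own rule therefore gives a boundary of 6 for N = 13 to 15.

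An exact recursion, checking after each patient, shows that Table 10 was computed for a maximum of 12:

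| Risk | Table 10 | Exact, maximum 12 | Exact, maximum 15 |
|---|---|---|---|
| 0.15 | 7.4%, N 11.5 | 7.6%, N 11.5 | 7.9%, N 14.3 |
| 0.30 | 39.8%, N 9.6 | 40.0%, N 9.6 | 43.5%, N 11.4 |
| 0.50 | 86.3%, N 6.1 | 86.1%, N 6.1 | 90.3%, N 6.5 |

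The small differences from the printed values are consistent with the 5000 simulations the plan used.

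**The case against.** The strongest reply is that the decision number is already stated. Section 13.5 holds the only go rule and names twelve patients; it allows 15 only as replacements, and the bracket in Section 3.0 points to the same intent. On that reading 12 is the target, 15 is the cap, and alpha stays at 0.049. Section 13.7 contains no go rule: it reports a proportion with a 90% confidence interval, and an estimate from 13 to 15 patients has no alpha to inflate. This is also a pilot whose positive result leads only to consideration of a larger study. Power rises along with alpha, and at the plan's own 20% allowance the averaged alpha is 0.049. Ascorbate starts on cycle 1 day 8 (Section 7.6.2), so a patient lost in week 1 counts as dosed under Section 3.0 but is not evaluable.

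Much of this stands. The target-and-cap reading is plausible and probably what was meant, the stated arithmetic is right, and the excess is small. But the Section 3.0 enrolment sentence is not conditional, and a patient replaced under Section 13.5 can remain evaluable under Section 13.7. Nothing says that the decision uses 12 patients when more are evaluable. The intended reading has to be inferred.

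**Conclusion.** The concern holds. The documents give 12 and 15 without a rule that turns one into the other, and the only go rule is calibrated for 12. If fewer than 3 of 15 dosed patients are unevaluable and the cut-off stays at 2, alpha at the 3% null is 0.056 (n = 13), 0.065 (n = 14) or 0.073 (n = 15, the maximum). That is 0.6 to 2.3 percentage points above the stated limit. With exactly 3 unevaluable there is no excess. If more are lost and not replaced, the problem reverses and power falls to 0.76 (n = 11) or 0.71 (n = 10).

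The alpha for each n needs only the plan's own p0 and cut-off. The chance of exceeding 12 and the averaged alphas rest on the assumed unevaluable rate.

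The safety point is secondary. The Section 13.6 rule already covers patients 13 to 15; only its tabulation and operating characteristics stop at 12. This should be fixed, but it does not undermine the design.

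**What to change.** Use one rule in Sections 1.0, 3.0, 13.5 and 13.7.

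- **Preferred.** The go decision uses the first 12 evaluable patients in order of enrolment, with evaluability as defined in Section 13.7. Up to 15 are enrolled only to replace unevaluable patients. An early drop-out is defined as a patient who is unevaluable under Section 13.7. Any further evaluable patients enter the estimate and its interval, but not the decision.
- **Alternative.** State that up to 15 may be analysed with a cut-off of 2, and give the error rates for each n, up to alpha 0.073 and power 0.89 at n = 15.

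Under either option more than 12 patients may be treated, because a replaced patient may already have been dosed. Extend Table 9 with the plan's own posterior rule (6 events for N = 13 to 15) and rerun Table 10 for a maximum of 15.

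**Cost.** Protocol and SAP wording and one rerun of Table 10; no design change. The preferred option keeps alpha at or below 0.049 but does not guarantee 12 evaluable patients. With a cap of 15 and 20% unevaluable (assumption), the chance of fewer than 12 is 35% and averaged power is 0.77; at 10% these are 6% and 0.80. The alternative requires the plan to state an alpha above 0.05.
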